5.5 STRATEGIES FOR RECRUITMENT AND RETENTION

RECRUITMENT:

- Potential enrollees will all be inpatients in the NICU at one of the participating hospitals.

All inpatients in the NICU born at \leq 30 weeks + 6 days postmenstrual age will be captured in the screening log, and beginning at 32 weeks + 0 days PMA, if they are being treated with routine caffeine, will be screened for potential eligibility. Screening will be discontinued whenever infants meet a specified exclusion criterion for enrollment or if they reach 36 weeks + 6 days PMA without meeting all inclusion criteria. It is estimated based on pilot studies that 30-50% of all screened infants will meet 1 or more exclusion criteria or fail to meet inclusion criteria. If an infant is a transfer from another facility at \leq 36+6, they WILL be added to the screening log. If they are a transfer from another facility at \geq 37+0, they WILL NOT be added to the screening log.

- The families of infants who are meeting enrollment criteria will be approached by study staff regarding possible enrollment.

RETENTION:

- As infants are approaching the time of discharge staff will utilize the pre-discharge checklist to:
 - Obtain detailed tracking information that provides information regarding where the infant will be cared for post-discharge and multiple methods to contact key family members
 - Provide and document comprehensive training of families regarding use of the oxygen saturation recorder
 - Provide and document training of families regarding giving study drug to their infant and using the home drug log
 - Provide and document training of families regarding obtaining and storing the saliva sample for caffeine levels
 - Provide and document training of families related to study expectations for future communication (i.e. telephone contacts) and study visits for the MRI, if necessary, and the end of study visit
- **Following discharge** families will be contacted within 1 – 3 days after discharge and then at least weekly to support families in performing study procedures including drug administration, **use of oximeter (if applicable)**, and ascertain any concerns about these procedures or the clinical status of the infant, including the occurrence of adverse events.
- The parents of each subject will receive gift cards for a total of \$100, at completion of their participation in the study. The purpose is to defray travel expenses for the return visit, if applicable, and for baby supplies, indicating our appreciation for their support of the collective protocol requirements.

6 STUDY INTERVENTION**6.1 STUDY INTERVENTION(S) ADMINISTRATION****6.1.1 STUDY INTERVENTION DESCRIPTION**

- The intervention for this study is the extended treatment of infants with caffeine, for evaluation of the efficacy of extended caffeine in ameliorating persisting **IH** and its adverse consequences including inflammation and brain MRI structural and functional injury. Caffeine is a standard treatment in preterm infants in the NICU, but currently is commonly discontinued between 32 and 36 weeks PMA. The FDA has granted an IND Exemption for the extended treatment with caffeine to 42 weeks + 6 days.

6.1.2 DOSING AND ADMINISTRATION

- The dose of caffeine base will be the same caffeine dose per kg as determined in our recent pilot study, both the QD starting dose and the BID dose at 36 weeks + 0 days PMA to adjust for increasing rates of metabolism.
- The caffeine doses used have been shown in our pilot study to be sufficient to achieve and maintain effective systemic concentrations for significant attenuation of **IH**
- The equal volume placebo will be identical in appearance to the caffeine

- Due to the relatively long half-life of caffeine, timing of doses may have some variance to best accommodate routine care and feeding schedules. The time of the 1st dose will be approximately 24 hours after the last routine clinical dose, and the subsequent QD doses will be given at the same approximate time each day, as consistent with daily care schedules. Timing of the BID doses starting at 36 weeks + 0 days PMA will be determined as consistent with daily care schedules, and will then be continued at the same times every day. After discharge, timing of the doses may initially be modified to be most consistent with home care schedules, and then repeated at the same approximate time(s) each day.
- All study drug will be given prior to a feeding.
- Study drug will be continued from the 1st dose, which will be given sometime between 32 weeks + 0 days and 36 weeks + 6 days PMA, through the last scheduled dose at 42 weeks + 6 days PMA.
- Study drug will be administered by clinical care personnel in the same manner as for routine caffeine use. Clinical care and/or research staff will teach parents how to administer so that administration at home will be comparable to that in the NICU.
- For home use, families will be instructed how to draw up the proper dose from the study drug vials supplied by research staff.
- Missed QD doses will be given as soon as possible after the missed dose, but that dose will be eliminated (and details recorded) if missed for more than 12 hours. For BID doses, missed doses will be given as soon as possible after the missed dose, but that dose will be eliminated (and details recorded) if missed for more than 6 hours.

6.2 PREPARATION/HANDLING/STORAGE/ACCOUNTABILITY

6.2.1 ACQUISITION AND ACCOUNTABILITY

Each clinical research site is responsible for procuring the required supplies needed to prepare blinded doses for both inpatient and outpatient doses. See Pharmacy Manual for specific compounding ingredients and instructions.

- Instructions will be provided to the parents/caregivers to administer the blinded oral doses just prior to the morning feeding and just prior to a late afternoon or early evening feed (breast or bottle). A diary will be provided for recording all administered doses.
- All used bottles and unused study solution will be returned to the research pharmacy (IDS) at study end.

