Endpoints:	
Primary:
 
 • Extent of IH as measured by seconds below 90% saturation per 24 hours of recorded oximetry data within each week PMA, and overall • Plasma concentration changes in inflammatory biomarkers between baseline and 38 weeks + 0 days PMA • MRI changes in microstructural measures between baseline and end of study (between 43 weeks + 0 days and 46 weeks + 6 days PMA). 
Secondary
 
 • #IH events per 24 hours of recorded oximetry data, # sec < 80% saturation per 24 hours of recorded oximetry data, nadir saturation during events, and the duration of events and area under of curve during events below 90% and 80% threshold saturation • Changes in inflammatory biomarkers and MRI measures of regional tissue volume between baseline and end of study in relation to IH measures
Study Population:	
Sample size: 220 infants, 110 caffeine and 110 placebo-treated
 
Gender: Male and female
 
Age: Enrollment at PMA 32 weeks + 0 days - 36 weeks + 6 days
 
Demographic Group: Infants born at \leq30 weeks + 6 days gestation
 
General Health Status: Clinically stable, on caffeine treatment and expected to receive last dose of routine caffeine treatment no later than 36 weeks + 5 days PMA
 
Geographic location: NICU or step down unit at a participating hospital, with final weeks at home following NICU discharge

Phase:	Not applicable
Description of Sites/Facilities Enrolling Participants:	Neonatal Intensive Care Units (NICU) in hospitals in metropolitan areas in the U.S. While inpatient the research will take place in the hospital. Once discharged, if the subject has been enrolled at a site performing MRIs, the patient will return to specified outpatient locations for performance of the follow-up MRI. At the end of the study, study termination procedures will be performed in a manner convenient for the family, and may be performed in person or remotely, and if applicable may be performed at the time of an MRI.
Description of Study Intervention:	Enrolled infants will be randomized to receive caffeine or equal volume placebo. The caffeine base dose will be 5 mg/kg once daily when the infant is at age 35 weeks + 6 days PMA or less. When the infant is at 36 weeks + 0 days PMA or more the caffeine base dose will be 5 mg/kg twice daily, based on the expected increased rate of caffeine metabolism that occurs as infants age.

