1.3 SCHEDULE OF ACTIVITIES (SOA)

Study Procedures	≤30 weeks + 6 days thru 36 weeks + 6 days	32 weeks + 0 days thru 36 weeks + 6 days	Target: 1 day post last routine caffeine dose (but window of up to 3 calendar days allowed)	1 week on study drug (up to 14 days post 1 st dose)	36 weeks + 0 days PMA	Hospital Discharge	40 weeks + 0 days PMA	42 weeks + 6 days PMA	43 weeks + 6 Days PMA
Screening	X								
Informed Consent		X							
Enrollment		X							
Baseline Data Collection		X							
Pulse oximetry recording						X ¹⁰			
Randomization			X						
Once daily study drug				X ¹					
Twice daily study drug							X ¹		
Drug log						X			
Saliva for caffeine level				X			X ²		
Biomarker blood sample		X ³				X ³			
MRI/MRS		X ⁴							X ⁴
Pre-discharge checklist						X ⁵			
Weekly parent phone contact							X ⁶		
Infant sleep Q								X ⁷	
End of study visit									X ⁸
Concomitant medications					X ⁹				
Adverse Event					X ⁹				

1. Study drug (caffeine base 5 mg/kg QD or placebo, weight adjusted weekly while in hospital) begins 1 day after last day of routine caffeine, but no later than the 3rd calendar day after last dose of routine caffeine. Dose is increased to 5 mg/kg BID at 36 + 0; finally, the last dose of study drug is at 42 + 6. Note that initial dose will be BID if enrolled at 36 + 0 or later.
2. 2nd caffeine level targeted at 40 + 0, (no earlier than 39 + 0 and no later than last day of study drug), whether in hospital or at home.
3. 1st biomarker blood sample should be obtained as close as possible to the day of randomization. Whenever possible, this blood sample should be timed with a clinically required blood draw. To facilitate obtaining this sample at the time of a clinical blood draw, this sample may be obtained at any time after consent, but no later than the 2nd calendar day after the first dose of study drug. The 2nd sample is to be obtained at 38 + 0 (+ or - 3 days) or within 2 calendar days prior to hospital discharge, whichever comes first.
4. 1st MRI/MRS is done in hospital sometime between enrollment and 3 calendar days after starting study drug. 2nd MRI/MRS is targeted at 43 + 0 but should be no later than 46 + 6. MRI visit may be combined with the end of study visit. MRI/MRS scans will only be performed for subjects enrolled at sites participating in the MRI/MRS portion of the study.

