4.3 JUSTIFICATION FOR DOSE

Infants will be started on oral caffeine base at 5 mg/kg/day or equivalent volume of placebo. At 36 weeks + 0 days PMA, study drug dose will be increased to 5 mg/kg BID (total daily dose 10 mg/kg) or equivalent volume of placebo. The dose will be weight-adjusted weekly until NICU discharge. The starting dose and dose escalation at 36 weeks + 0 days PMA reflect increasing clearance rates that have been established in pilot studies as being appropriate to achieve caffeine levels within the most likely therapeutic range. All subjects will be on enteral medications when enrolled.

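### Section 6.2.1 tells parents to dose morning and evening with no PMA condition, which contradicts once-daily dosing through 35+6 for infants who go home before 36+0 (minor wording error)

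*Combined protocol and SAP*

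**What the plan says.** The parent instruction is a bullet in Section 6.2.1 (Acquisition and Accountability). Parents or caregivers will be told to "administer the blinded oral doses just prior to the morning feeding and just prior to a late afternoon or early evening feed". The two feed times are joined by *and*, and no PMA is mentioned.

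The dosing rule appears elsewhere, consistently:

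- Section 1.1 (Description of Study Intervention): "The caffeine base dose will be 5 mg/kg once daily when the infant is at age 35 weeks + 6 days PMA or less". The same entry gives 5 mg/kg twice daily from 36+0.
- Section 1.3, footnote 1: "Dose is increased to 5 mg/kg BID at 36 + 0".
- Section 4.3: "At 36 weeks + 0 days PMA, study drug dose will be increased to 5 mg/kg BID", a daily total of 10 mg/kg.
- Section 6.1.2 has the same once-daily and twice-daily schedule and covers the home period. After discharge, doses are to be "repeated at the same approximate time(s) each day". There is a separate once-daily rule, "Missed QD doses will be given as soon as possible after the missed dose". Parents are to be taught so that "administration at home will be comparable to that in the NICU". On feeds it says only: "All study drug will be given prior to a feeding".

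None of these sections makes an exception for infants at home, and nothing limits the Section 6.2.1 bullet to infants at or beyond 36+0.

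**The concern.** Section 6.2.1 is the protocol's specific statement of what parents will be told about when to dose. Taken at its word, it puts an infant on two doses a day from the day of discharge. That is right from 36+0 and wrong before it.

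Infants at home before 36+0 are foreseeable. Section 1.1 gives 34 to 40 weeks PMA as the usual discharge range, and Section 6.2.2 starts outpatient supply at discharge, whatever the PMA. Under the routine-caffeine guideline in Section 6.5, caffeine stops at 34 weeks at the latest, so many infants should begin study drug early enough to have once-daily days left.

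The instruction matters more at home than in hospital. Inpatient doses come from pharmacy as a 24-hour supply in unit-dose syringes. Families hold bulk solution meant to last to 42+6 and draw up each dose themselves, so the supply would not prevent a second daily dose. An infant who goes home on once-daily dosing must also change to twice daily at home, and the bullet does not mention that change.

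At stake is a doubled daily caffeine dose in the active arm on home days before 36+0. Placebo infants would get extra volume only.

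**Working it through.** **Inputs.** Dose per administration 5 mg/kg; once daily to 35+6, twice daily from 36+0 to 42+6 (Sections 1.1, 1.3, 4.3). Usual discharge range 34 to 40 weeks, with about half of study time as an inpatient (Section 1.1; Section 6.4 is similar). First saliva sample taken in the NICU one week after starting study drug (Section 8.1.4). Routine caffeine stopped by 34 weeks under the guideline (Section 6.5). Study drug started 1 to 3 calendar days after the last routine dose (Section 1.3).

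**The plan's own figure.** 5 mg/kg × 2 = 10 mg/kg/day, which matches Section 4.3. Before 36+0 the intended dose is 5 × 1 = 5 mg/kg/day, so the literal bullet doubles it.

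**Formulas.**
- Extra doses = days at home before 36+0 = 36+0 minus PMA at discharge.
- Extra caffeine base = extra doses × 5 mg/kg.
- Scheduled doses = once-daily days from start to 35+6, plus 49 days × 2 = 98.

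**Assumption.** The PMA at discharge is not given for any infant. The cases below assume discharge right after a saliva sample taken on day 7.

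| Start | Home | Extra doses | Extra base, mg/kg | Scheduled doses | Share |
|---|---|---|---|---|---|
| 33+0 | 34+0 | 14 | 70 | 21 + 98 = 119 | 11.8% |
| 34+1 | 35+1 | 6 | 30 | 13 + 98 = 111 | 5.4% |
| 34+3 | 35+3 | 4 | 20 | 11 + 98 = 109 | 3.7% |
| 34+6 | 35+6 | 1 | 5 | 8 + 98 = 106 | 0.9% |

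The first row is the early edge of the usual discharge range. Rows two and three are starts one and three days after a last routine dose at 34+0. With a day-7 sample, the latest start that leaves any once-daily day at home is 35+6 minus 7 days = 34+6. Section 1.3 allows the sample up to day 14; if discharge waited for that, the latest such start would be 35+6 minus 14 days = 33+6.

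**Typical case.** Suppose half of the study-drug period, to 42+6, is spent in hospital. A start at 32+0 gives 76/2 = 38 days and discharge at about 37+3. A start at 34+1 gives 61/2 = 30.5 days and discharge at about 38+3 to 38+4. Both are after 36+0, so there are no extra doses.

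The mg/kg totals are nominal. Sections 1.3 and 4.3 adjust the dose for weight only while in hospital, so a fixed home volume delivers somewhat less than 5 mg/kg as the infant grows.

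**The case against.** The strongest reply is that the bullet sits in an accountability section, names no frequency or mg/kg dose, and only says when to give doses that Section 6.1.2 has just defined. On that reading it gives feed times for the twice-daily schedule, which is the usual one at home, and merely lacks a qualifier. To misdose, a site would have to follow this one bullet against a rule repeated in four other sections.

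There are also safeguards. Families are contacted within a few days of discharge and at least weekly, and the calls cover the drug log and administration problems (Sections 5.5, 6.4, 8.2.1). Pharmacy records the outpatient dose and quantity (Section 6.2.3). The 14-dose case would have to survive at least two contacts. The scenarios also rest on an assumed discharge date, and the documents withhold nothing to show that any handout is wrong, because the handout, Pharmacy Manual and Manual of Procedures are not available.

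Much of this stands. The governing rule is clear, the typical infant is unaffected, the calls may catch an error early, and the dose counts are illustrations. These points keep the matter minor. They do not make the sentence right: it says what parents will be told, it names two doses joined by *and*, and a site drafting a handout would naturally turn to it.

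**Conclusion.** The concern holds, as a minor wording error. As written, Section 6.2.1 contradicts once-daily dosing through 35+6 for any infant at home before 36+0. Followed literally, it adds one 5 mg/kg dose per home day before 36+0 in the caffeine arm: 1 to 6 extra doses in the day-7 cases with starts from 34+1 to 34+6, 14 at the early edge of the usual discharge range, and none in the typical case. The share of infants discharged before 36+0 is not given, so no number affected can be stated.

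Serious harm is not shown, since 10 mg/kg/day is the trial's own dose from 36+0. The effect on the main comparison is limited: the sample size in Section 9.2 rests on weeks 36 to 42, the extra doses fall before that, and home oximetry runs only at participating sites (Section 8.1.1). No sample size, power or analysis rule changes.

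**What to change.** Reword the Section 6.2.1 bullet so that parents are told to dose once daily, before a feed, through 35 weeks + 6 days PMA, and twice daily, at the two feed times already named, from 36 weeks + 0 days PMA. This agrees with Sections 1.1, 1.3, 4.3 and 6.1.2. The sponsor should also check that site handouts and the Pharmacy Manual give the same two-step schedule.

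The cost is one reworded bullet, with no change to design, procedures, forms or analysis.

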6.2.2 DOSE PREPARATION, AND LABELING

Inpatient Doses: *Caffeine base or Placebo*

Caffeine base: IDS pharmacies will prepare a bulk oral solution containing caffeine base (anhydrous) 10 mg/mL, according to the instructions in the Pharmacy Manual. A bulk solution can be prepared individually for a patient or can be used for multiple patients (preferred) who are assigned/randomized to receive active treatment.

A 24 hour supply is prepared from the bulk solution and dispensed in a suitable-sized unit-dose, oral syringe. All oral syringes prepared and administered in the inpatient setting are to be labeled in a blinded fashion, using specific departmental procedures for labeling of blinded syringes and reflecting blinded

study drug information on the medication administration record (e.g. eMAR). All syringes must be labeled as “For Investigational Use Only” (or alternative site specific verbiage to identify a study medication). Syringes can be prepared as long as 4 days prior to administration (BUD 4 days) and should be stored at room temperature.

Example: Caffeine base 10 mg/1 mL or Placebo; Caffeine base 10 mg or placebo (1 mL)

Placebo: Research pharmacies will prepare a bulk oral solution according to instructions in the pharmacy manual. A bulk solution can be prepared individually for a patient or can be used for multiple patients (preferred) who are assigned/randomized to receive placebo treatment.

A 24 hour supply is prepared from the bulk solution and dispensed in a suitable-sized unit-dose, oral syringe. All oral syringes prepared and administered in the inpatient setting are to be labeled in a blinded fashion, using specific departmental procedures for labeling of blinded syringes and reflecting blinded study drug information on a medication administration record (e.g. eMAR). All syringes must be labeled as “For Investigational Use Only” (or alternative site specific verbiage to identify a study medication). Syringes can be prepared as long as 4 days prior to administration (BUD 4 days) and should be stored at room temperature.

Example: Caffeine base 10 mg/1 mL or Placebo; Caffeine base 10 mg or placebo (1 mL)

Outpatient Doses:

Doses intended for outpatient administration, starting at time of discharge and continuing until 42 weeks + 6 days PMA, are prepared by the IDS pharmacy at each clinical site and issued as a bulk solution containing a sufficient quantity of either the active drug (caffeine base) or placebo to last until 42 weeks + 6 days (BUD 90 days).

6.2.3 PRODUCT STORAGE AND ACCOUNTABILITY

IDS pharmacies are temperature controlled and have access limited to pharmacy personnel only. Compounding and accountability records are maintained by the IDS pharmacy to reflect drug preparation and dispensing for patients receiving both the active and placebo solutions, prepared for both inpatient and outpatient treatment. All supplies used to prepare both the active and placebo oral solutions are to be stored in the IDS/research pharmacy, in accordance with temperature parameters indicated on the product label.

Sites may use/develop their own accountability forms; specific information to be documented on the drug accountability record includes: patient initials, patient study ID number, individual dose (mg per mL), lot number and beyond use date of the prepared solution. For outpatient dosing, the quantity dispensed (mLs), the dose and the dispensing date must also be recorded. The use of an electronic record (e.g., Vestigo) is acceptable as long as the required information is captured, including patient-returned medication.

Any remaining doses of study drug not administered at home are to be returned by the family member during the end-of-study outpatient visit if applicable, or sent back, and eventually returned to the IDS pharmacy for on-site destruction following reconciliation and accountability of the unused doses. Used bottles are to be returned to the IDS pharmacy; if remaining solution is present, it is to be measured and recorded as a return. Empty bottles are to be recorded as zero mL. Once the information for the returned bottle has been recorded, the solution and bottle can be disposed of as non-hazardous pharmaceutical waste, according to institutional procedures.

6.3 MEASURES TO MINIMIZE BIAS: RANDOMIZATION AND BLINDING

Randomization:

- Ideally one day following, but up to the third calendar day following the last routine caffeine treatment dose, enrolled infants will be randomized in a 1:1 ratio to 1 of 2 treatment arms, caffeine base or placebo.
- Infants from multiple births will be cluster randomized.
- A site-stratified randomly-permuted blocked randomization design will be used to ensure balance at each site.
- To ensure balance by gestational age at birth, randomization will also be stratified into 2 birth gestational age categories: 1) <28 weeks and 2) 28 weeks + 0 days through 30 weeks + 6 days gestation.
- A randomization scheme will be developed by the DCC using specialized software, and clinical sites will be provided appropriate enrollment logs and blinded randomization procedures.

Blinding:

- Treatment assignments will be blinded until study completion for all study personnel, except for the clinical site research pharmacy dispensing study drug.
- The study pulse oximeter will not have visual displays or alarms for respiration or heart rate activated during the study period ending at 43 weeks + 6 days. The **IH** which is the focus of study typically does not result in overt apnea or bradycardia, and therefore we do not anticipate a need for unblinding based on oximeter results
- Any requests for unblinding will be adjudicated by one of the study Principal Investigators, and can only be authorized by them.
- Two salivary caffeine concentrations are being obtained from all subjects, but the results of the caffeine concentrations will be blinded until all infants have completed the study protocol.
- Potential caffeine side effects, such as mild tachycardia, irritability or feeding difficulties are frequent in both caffeine-treated non-treated infants. If such concerns arise, however, at the discretion of the clinical care team, study drug may be held for the days necessary, and noted in study records, but would generally not be a reason to request unblinding.
- If apnea-related symptoms requiring treatment occur after starting study drug, the clinical care team may institute treatment as needed until cessation of these symptoms, and similarly, this also should not require unblinding.

